17.2 Study Endpoints and Analytic Plan

All subjects who receive at least one dose of study drug will be considered evaluable and included in the efficacy and safety analysis.

Definition of primary outcome/endpoint:

The primary endpoint is the overall response rate defined as the best response within the first 24 weeks of the start of study therapy using RECIST v. 1.1 that has been confirmed at a subsequent time point (≥ 4 weeks).

Definition of secondary outcomes/endpoints:

PFS is defined as time from enrollment to time of clinical or radiographic disease progression as defined by RECIST v.1.1 criteria. OS is defined as time from enrollment to time of death from any cause.

Analytic plan for primary objective:

The overall response rate will be summarized using point estimates and 95% confidence intervals.

Analytic plan for secondary and exploratory objectives:

- We will estimate the survival distribution for both PFS and OS endpoints using the Kaplan Meier method. The log rank test will be used to examine differences between survival curves using prognostic markers.
- For correlative studies we will apply either the Fisher's exact test or Wilcoxon Rank Sum test to examine the associations between response status and changes in markers expression for categorical and continuous variables, respectively. Because of the limited sample size, the biomarker data analysis is for exploratory research only.
- Toxicity data will be summarized by type, frequency, and severity according to the NCI CTCAE criteria v4.0.

- Pharmacokinetic and pharmacodynamic parameters will be summarized using descriptive statistics and graphical methods (individual profile plots).

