15. MEASUREMENT OF EFFECT

15.1 Antitumor Effect – Solid Tumors

For the purposes of this study, patients should be re-evaluated for response every 8 weeks weeks. In addition to a baseline scan, confirmatory scans should also be obtained 4 of weeks weeks following initial documentation of objective response.

Response and progression will be evaluated in this study using the international criteria proposed by the revised Response Evaluation Criteria in Solid Tumors (RECIST) guideline (version 1.1) [Eur J Ca 45:228-247, 2009]. Changes in the largest diameter (unidimensional measurement) of the tumor lesions and the shortest diameter in the case of malignant lymph nodes are used in the RECIST criteria.

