15.2 Definitions

Evaluable for toxicity: All patients will be evaluable for toxicity from the time of their first treatment with ruxolitinib.

Evaluable for objective response: Only those patients who have measurable disease present at baseline, have received at least one cycle of therapy, and have had their disease re-evaluated will be considered evaluable for response. These patients will have their response classified according to the definitions stated below. (Note: Patients who exhibit objective disease progression prior to the end of cycle 1 will also be considered evaluable.)

Evaluable Non-Target Disease Response: Patients who have lesions present at baseline that are evaluable but do not meet the definitions of measurable disease, have received at least one cycle of therapy, and have had their disease re-evaluated will be considered evaluable for non-target disease. The response assessment is based on the presence, absence, or unequivocal progression of the lesions.

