17. STATISTICAL CONSIDERATIONS

17.1 Study Design and Sample Size

This is a multi-center, non-randomized, open-label phase 2 trial to evaluate the efficacy and safety of ruxolitinib in post-transplant patients with advanced cutaneous squamous cell carcinoma. The primary endpoint is overall response rate, defined as the best response confirmed

within the 24 weeks of the start of study therapy.

We will use a Simon Two-Stage Min-Max design with a target overall response rate of 20% (alternative hypothesis), compared to a historical response rate of 5% (null hypothesis) with chemotherapy, with one-sided probability of a type I error set at 0.10 and power of 90%. In the first stage, 18 patients will be accrued. If less than 1 patient achieves a response among the initial 18 patients, the study will be declared negative and terminated. If at least 1 patient achieves a response, an additional 14 patients will be accrued to the second stage for a total of 32 evaluable patients. Overall, if 4 or fewer responses are seen, the study will be declared negative. If at least 5 total patients achieve a response, that treatment will be declared positive for attaining the primary endpoint. There is a 40% chance of stopping at Stage 1 if the true confirmed response rate is at most 5% (null hypothesis). Accounting for 10% dropout, we will plan to enroll a total of 35 patients unless a second safety lead-in is required, in which case the the maximum potential accrual will be 41 patients.

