17.5.2 Evaluation of response

All patients included in the study will be assessed for response to treatment, even if there are major protocol treatment deviations or if they are ineligible. Each patient will be assigned one of the following categories: 1) complete response, 2) partial response, 3) stable disease, 4) progressive disease, 5) early death from malignant disease, 6) early death from toxicity, 7) early death because of other cause, or 9) unknown (not assessable, insufficient data).

All of the patients who met the eligibility criteria (with the possible exception of those who received no study medication) will be included in the main analysis of the response rate. Patients in response categories 4-9 should be considered to have a treatment failure (disease progression). Thus, an incorrect treatment schedule or drug administration does not result in exclusion from the analysis of the response rate. Precise definitions for categories 4-9 will be protocol specific.

All conclusions will be based on all eligible patients. Subanalyses may then be performed on the basis of a subset of patients, excluding those for whom major protocol deviations have been identified (e.g., early death due to other reasons, early discontinuation of treatment, major protocol violations, etc.). However, these subanalyses may not serve as the basis for drawing conclusions concerning treatment efficacy, and the reasons for excluding patients from the analysis should be clearly reported. The 95% confidence intervals should also be provided.

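### Sections 15.2, 17.2 and 17.5.2 give three different patient sets for the primary response rate, and the 18 and 32 of the decision rule are not tied to any of them.

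*Combined protocol and SAP*

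**What the plan says.** **Decision rule (17.1).** The trial stops if none of the first 18 patients responds. Otherwise 14 more are accrued "for a total of 32 evaluable patients". The same paragraph adds: "Accounting for 10% dropout, we will plan to enroll a total of 35 patients". Sections 17.1 and the synopsis require at least 5 responses for a positive result, while 5.2 implies at least 4. That conflict is a separate matter, so both cut-offs are carried below.

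**Efficacy set (17.2).** "All subjects who receive at least one dose of study drug will be considered evaluable and included in the efficacy and safety analysis".

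**Evaluable for objective response (15.2).** "Only those patients who have measurable disease present at baseline, have received at least one cycle of therapy, and have had their disease re-evaluated" qualify. A note adds patients with objective progression before the end of cycle 1.

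**Main response analysis (17.5.2).** It covers patients who met the eligibility criteria, with a possible exception for those never dosed. Progressive disease, early death and not assessable all count as treatment failure. Subset analyses that leave out early deaths or early discontinuations are allowed, but "these subanalyses may not serve as the basis for drawing conclusions concerning treatment efficacy". The section also says: "All conclusions will be based on all eligible patients".

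**The concern.** The primary endpoint is a proportion in a single-arm, open-label trial, so its denominator should be fixed before responses are known. Here one word, evaluable, has two meanings, and a third set (eligible patients) carries the conclusions.

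The patients who separate 15.2 from 17.2 are mainly those who stop or die in cycle 1 without documented progression, and those who die before any re-evaluation. Section 15.1 says "patients should be re-evaluated for response every 8 weeks", so the first planned scan is at week 8. Such patients cannot have a confirmed response. Removing them can only raise the reported rate.

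Section 17.2 has a gap of its own. If all 35 enrolled patients are dosed, all 35 are evaluable, yet the rule is written for 32.

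**Working it through.** **1. The three sets side by side**

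| Patient | 15.2 | 17.2 | 17.5.2 |
|---|---|---|---|
| Eligible, one cycle or more, re-evaluated | in | in | in |
| Eligible, objective progression before end of cycle 1 | in | in | in, failure |
| Eligible, stops or dies in cycle 1, no documented progression | out | in | in, failure |
| Eligible, completes cycle 1, dies before any re-evaluation | out | in | in, failure |
| Dosed but ineligible, measurable disease, one cycle, re-evaluated | in | in | assessed, but not in main analysis |
| Eligible, never dosed | out | out | left open |

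**2. Reproducing the plan (17.1, 5.2)**

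Inputs: null 5%, target 20%, n1 = 18 with a stop at 0 responses, N = 32, cut-off k = 4 (5.2) or k = 5 (17.1).

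Stop at stage 1 = (1 − p)^18. At 5%: 0.95^18 = 39.7%, matching the stated 40%.

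P(positive) = P(X32 ≥ k) − (1 − p)^18 × P(X14 ≥ k), where Xn is binomial(n, p). At p = 0.05 and k = 4: 0.0738 − 0.0017 = 0.0721.

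| Cut-off | Type I error at 5% | Power at 20% |
|---|---|---|
| at least 4 | 7.21% | 90.15% |
| at least 5 | 2.02% | 79.33% |

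**3. Effect on the estimate**

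If a share f of dosed patients is excluded and none of them responded, the rate is multiplied by 1/(1 − f). The documents give no value for f. Taking 3 of 35 (8.6%) and five responses: 5/35 = 14.3% and 5/32 = 15.6%. The difference is 1.3 percentage points, and 35/32 − 1 = 9.4% relative. At f = 5%, 10% and 15% the relative overstatement is about 5%, 11% and 18%.

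**4. Effect on the decision, only if excluded patients are replaced**

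For a fixed group of patients the response count is the same under either definition. The decision can differ only if more patients are dosed until 18 or 32 meet 15.2. Assume also that the 5% null applies to all dosed patients. The rate among evaluable patients is then q = 0.05/(1 − f), put into the formulas of step 2.

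| f | q | Stop at stage 1 | Type I error, at least 4 | Type I error, at least 5 |
|---|---|---|---|---|
| 0 | 5.00% | 39.7% | 7.2% | 2.0% |
| 10% | 5.56% | 35.7% | 9.7% | 3.0% |
| 15% | 5.88% | 33.6% | 11.4% | 3.7% |
| 20% | 6.25% | 31.3% | 13.4% | 4.7% |

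**5. All 35 enrolled are dosed under 17.2**

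Keeping stage 1 at 18 and applying the final cut-off to 35 gives type I error of 9.2% (at least 4) or 2.9% (at least 5), against 7.2% and 2.0% at 32.

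**The case against.** The strongest reply is that Section 17 already answers the question. Section 17.2 follows 17.1 directly, uses the same word and assigns it to the efficacy analysis. Section 17.5.2 counts unassessable patients as failures and bars subsets from supporting the conclusion. Section 15.2 belongs to the measurement chapter and can be read as saying only whose response is classified under RECIST. Most of this stands. A reader might infer that the plan leaves the governing set wholly open. It does not: Section 17 points to all treated patients. What remains is that 15.2 is worded as an exclusive rule, 17.5.2 says eligible rather than treated, and neither the 18 nor the 32 is cross-referenced to a set.

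A reader might also take the 10% dropout allowance as proof that 15.2 was meant and that unassessable patients will be replaced. The documents do not support that. Registration precedes treatment (7.1), and the same section provides for patients who withdraw before therapy starts, so the allowance also fits loss before the first dose. No section provides for replacing dosed patients.

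The affected group is also narrow. Measurable disease is an entry criterion (6.1), early progressors remain evaluable under 15.2, and the end-of-treatment evaluation (13.2) will recover some patients.

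**Conclusion.** The inconsistency is real and should be fixed; its expected effect is modest. Using 15.2 would overstate the response rate by about 1.3 percentage points in the example, and the share excluded is an assumption.

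It would be too strong to say that the trial's type I error exceeds 10%. Among the cases computed, that happens only when three conditions hold together: dosed patients are replaced, the 5% null refers to all dosed patients, and the cut-off is at least 4 with 15% or more excluded. With at least 5 responses the error stays below 5% even at 20% excluded. If the historical 5% was itself measured in evaluable patients, there is no inflation; the documents do not say. Nor can it be said without qualification that the error stays within 10%.

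The open treatment of patients 33 to 35 under 17.2 needs no replacement assumption. It keeps the error within 10% at either cut-off.

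**What to change.** - In 17.1 and 17.2, state that the primary efficacy set is all treated patients and that anyone without a post-baseline assessment is a non-responder.
- In 17.5.2, change the eligible-patient wording to match.
- Limit 15.2 to RECIST classification, or label its set a sensitivity analysis that cannot support the efficacy conclusion.
- Pre-specify how the rule treats patients dosed after the 32nd. One option is to base the two decisions on the first 18 and first 32 treated patients, with later patients entering only the estimate and interval.
- State whether the 5% and 20% rates refer to treated or assessable patients.

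The cost is wording, with no extra patients, and possibly a slightly lower reported rate. There may also be a cost in power. If the 20% target refers to assessable patients and 10% are unassessable, the all-treated rate is 0.20 × 0.90 = 18%. Power at 32 treated is then 84.61% instead of 90.15% (at least 4), or 70.43% instead of 79.33% (at least 5).

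A separate minor point is to reconcile 5.1, which places the safety lead-in before stage 1, with 5.3.1, which equates stage 1 with the first 18 enrolled. The planned total suggests that lead-in patients count, since 6 + 32 = 38 exceeds 35, but the text should say so.

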| Reference therapy | Historical response rates to chemotherapy in advanced cutaneous squamous cell carcinoma in transplant recipients (reference response rate 5-10%) |
| Statistical Methodology | 
Definition of primary outcome/endpoint: The primary endpoint is the overall response rate as defined as the best response, confirmed at ≥ 4 weeks, within the first 24 weeks of the start of study therapy, using RECIST v1.1 criteria.
 
Definition of secondary outcomes/endpoints: PFS is defined as time from registration to time of clinical or radiographic disease progression as defined by RECIST v1.1 criteria, or death. OS is defined as time from registration to time of death from any cause.
 
Analytic plan for primary objective: We will estimate the response rate to ruxolitinib using the exact 95% confidence interval based on the binomial distribution.
 
Analytic plan for secondary and exploratory objectives:
 
• We will estimate the survival distribution for both PFS and OS endpoints using the Kaplan Meier method. The log rank test will be used to examine differences between survival curves.• For correlative studies we will apply either the Fisher's exact test or Wilcoxon rank sum test to examine the correlation between response status and markers for categorical and continuous variables, respectively. 
Sample size justification: We will utilize a Simon mini-max two-stage design in which a 5% RR is considered not promising, a 20% RR is considered promising, and the probabilities of a type I error (falsely accepting a non-promising therapy) and type II error (falsely rejecting a promising therapy) are set at 0.10 and 0.10, respectively. Eighteen patients with advanced cSCC will be accrued in the first stage. If 1 or more patients achieve a response, then an additional 14 will be accrued. If 4 or fewer responses are seen, the study will be declared negative.
 |

Protocol Schema:

[figure not shown]

Table of Contents

| | | |
|-----|---|----|
| 1. | Protocol Signature Page | 3 |
| 1. | Introduction..... | 12 |
| 2. | Study Objectives | 12 |
| 2.1 | Primary Objective | 12 |
| 2.2 | Secondary Objectives..... | 12 |
| 2.3 | Exploratory Objectives | 13 |
| 3. | Background | 13 |
| 3.1 | Cutaneous Squamous Cell Carcinoma | 13 |
| 3.2 | Rationale for JAK inhibition in advanced cutaneous squamous cell carcinoma..... | 13 |

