15.7 Progression-Free Survival

PFS is defined as the duration of time from start of treatment to time of progression or death, whichever occurs first.

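### PFS is timed from registration/enrollment in two places and from start of treatment in a third; with an all-treated analysis set, the pre-dose origin adds event-free time to PFS and OS

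*Combined protocol and SAP*

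**What the plan says.** The combined protocol and SAP defines PFS in three places:

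- Synopsis, Statistical Methodology: "PFS is defined as time from registration to time of clinical or radiographic disease progression". The sentence goes on to count death as an event.
- Section 15.7: "PFS is defined as the duration of time from start of treatment to time of progression or death, whichever occurs first".
- Section 17.2: "PFS is defined as time from enrollment to time of clinical or radiographic disease progression". This sentence refers to RECIST v1.1 and ends without mentioning death.

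OS is defined twice. The synopsis has "OS is defined as time from registration to time of death from any cause" and section 17.2 has "OS is defined as time from enrollment to time of death from any cause". Section 15.7 does not define OS.

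The analysis set is also in section 17.2: "All subjects who receive at least one dose of study drug will be considered evaluable and included in the efficacy and safety analysis". Both endpoints are estimated by Kaplan-Meier. The primary endpoint, response within 24 weeks, is counted from the start of study therapy in both the synopsis and 17.2. No text ranks the PFS definitions or says that registration, enrollment and first dose fall on the same day.

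**The concern.** Two analysts who each follow the protocol faithfully could report different PFS from the same data. The difference would not be neutral. If the clock starts before first dose but only dosed patients are counted, every analysed patient contributes a stretch at the front in which death is impossible. This is a small immortal-time bias, and it always favors the drug.

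PFS and OS are the only measures of clinical benefit named in the secondary objectives. The trial has one arm, so no control group shares the shift and cancels it; any comparison with outside figures carries it in full. PFS from registration would also run on a different clock from the response endpoint.

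**Working it through.** The plan gives no median, event count or power for PFS or OS, so there is no figure of its own to reproduce. The check has two parts.

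**1. Order of events, from the text**

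- Section 7.1 forbids protocol therapy before the central registration notice is received; section 21.5 says the same for affiliate sites. The synopsis (duration of administration) has treatment follow enrollment. Registration/enrollment therefore precedes first dose.
- The notice in 7.1 also carries enrollment status, so registration and enrollment are probably one event. The contrast that matters is registration/enrollment against first dose.
- Section 17.2 admits only dosed patients. An analysed patient cannot have died before first dose.
- Section 9.1 requires no evidence of progression on Day 1 of each cycle. Under that rule an analysed patient should have no recognised progression before first dose either.
- Section 12.1 limits screening, defined as consent to first dose, to 28 days. Registration comes after consent, so the registration-to-dose lag is at most 28 days. Section 7.1 allows same-day registration case by case, so it can be close to 0.

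**2. Size of the shift**

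Let *L* be the lag, taken as constant, and *S*_D the survival function from first dose. Measured from registration:

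- *S*_R(*t*) = 1 for *t* ≤ *L*, and *S*_R(*t*) = *S*_D(*t* − *L*) for *t* > *L*;
- median from registration = median from first dose + *L*;
- relative increase = *L* / median from first dose.

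With 30.44 days per month, 7, 14 and 28 days are 0.23, 0.46 and 0.92 months. The PFS medians below are assumptions; the documents give none. The 6-month PFS values also assume an exponential curve with median *m*: 0.5^(6/*m*) from first dose and 0.5^((6 − *L*)/*m*) from registration.

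| Assumed median PFS from first dose | Lag | Median from registration | Increase | 6-month PFS, first dose → registration |
|---|---|---|---|---|
| 3 months | 7 days | 3.23 | 8% | 0.250 → 0.264 |
| 3 months | 14 days | 3.46 | 15% | 0.250 → 0.278 |
| 3 months | 28 days | 3.92 | 31% | 0.250 → 0.309 |
| 6 months | 7 days | 6.23 | 4% | 0.500 → 0.513 |
| 6 months | 14 days | 6.46 | 8% | 0.500 → 0.527 |
| 6 months | 28 days | 6.92 | 15% | 0.500 → 0.556 |

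For OS, sections 1 and 3.1 cite a median survival of 3 years (36 months) from diagnosis of metastasis. A 28-day lag adds 0.92/36 = 2.6%. That benchmark runs from diagnosis, not from study entry, so the relative effect would be larger if survival from entry is shorter. The absolute shift stays at or below 28 days.

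**The case against.** The case for leaving this alone has several parts, and much of it stands.

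- **Number of origins.** A reader might infer three competing origins for PFS and two for OS. The documents do not support that count. Section 7.1 puts registration and enrollment in one notice, which leaves two real origins for PFS. For OS the wording differs but nothing contradicts a registration origin, so for OS the issue is only the lag.
- **Size.** A reader might infer inflation of 25% to 50%, by setting 4 weeks against a median of 16 or 8 weeks (4/16 and 4/8). The 28 days in 12.1 is a ceiling counted from consent, not the registration lag. It is approached only if the clock starts at the pending entry, which is requested within 48 hours of consent, and not at completed registration after eligibility review. The 8- and 16-week medians have no source in the documents.
- **Variation by site.** Affiliates have an extra forwarding step in 21.5, but no timing is given, so a site difference is possible and not shown.
- **Consequences.** The primary endpoint and the Simon rule use response timed from start of therapy. PFS and OS have no threshold, null value or power. The only planned test is a log-rank comparison by prognostic marker, and nothing suggests that the lag depends on the marker.
- **Population.** For response, 17.5.2 bases conclusions on all eligible patients and excludes the never-dosed only as a possible exception. Timing from registration would be coherent if all registered patients were analysed.

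These arguments limit the point without removing it. Section 15.7 still contradicts the synopsis and 17.2 for PFS, and the set stated in 17.2 is all-treated, which is the set that makes a pre-dose origin biased.

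**Conclusion.** The point holds in this limited form. PFS has two conflicting origins, registration/enrollment and start of treatment. OS has one origin, which precedes first dose. Paired with the all-treated set, the pre-dose origin lengthens both endpoints by the registration-to-dose lag, always in the drug's favor.

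The lag is unknown: between 0 and 28 days, possibly only days. The effect on PFS is therefore modest for short lags and material only near the ceiling with a short median. The effect on OS is small against the cited benchmark. The percentages rest on assumed PFS medians and a constant lag; if lags vary between patients, the curve is smeared as well as shifted. It would be wrong to infer that the trial's go/no-go decision is affected. This should be corrected because the bias runs one way in a single-arm trial and is easy to remove.

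**What to change.** - In the synopsis and section 17.2, define both PFS and OS from the first dose of ruxolitinib. This matches 15.7, the all-treated set and the 24-week response window.
- In the same 17.2 sentence, add death as a PFS event, as the synopsis and 15.7 have it. Read literally, 17.2 now describes time to progression, and changing the origin alone would not repair that.
- List patients who were registered but never dosed, and report the distribution of the registration-to-dose lag, so that readers can judge what the choice of origin is worth.

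Keeping registration as the origin is the other coherent choice, but it would require analysing every registered patient and changing 15.7 and the 17.2 analysis set.

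The cost is wording. Reported PFS and OS become slightly shorter than under a registration origin; sample size, the primary analysis and the stopping rule do not change. The origin should be settled before PFS and OS are analysed.

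### The planned response-rate estimate and 95% interval ignore the stop at 0 of 18; this is negligible at the success boundary but visible when only 1 or 2 of 32 patients respond

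*Combined protocol and SAP*

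**What the plan says.** Section 17.1 specifies a Simon two-stage minimax design with a null rate of 5%, a target rate of 20%, and "one-sided probability of a type I error set at 0.10 and power of 90" per cent. The early stop reads: "If less than 1 patient achieves a response among the initial 18 patients, the study will be declared negative and terminated". Otherwise "an additional 14 patients will be accrued to the second stage for a total of 32 evaluable patients".

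For reporting, Section 17.2 states only: "The overall response rate will be summarized using point estimates and 95% confidence intervals". It names no method. The synopsis (Statistical Methodology) does, calling for the "exact 95% confidence interval based on the binomial distribution". Section 17.5.2 also asks for 95% intervals. No section mentions an estimate or interval that takes the two stages into account.

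Two related items are inconsistent. Section 17.1 and the synopsis declare the trial negative at 4 or fewer responses; Section 5.2 does so at 3 or fewer. Section 17.1 counts 32 evaluable patients, while Section 17.2 treats every dosed patient as evaluable and 35 are to be enrolled.

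**The concern.** An ordinary binomial estimate and interval treat the 32 patients as one fixed sample. In this design a total over 32 patients exists only if at least one of the first 18 responded. One response among 32 therefore means one response among the first 18 and none in the next 14; the reverse pattern cannot occur. The raw proportion ignores that selection. Trials stopped at 0 of 18 contribute zeros that later patients cannot correct, so the raw rate is too low on average.

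What is at stake is how a weak result is described. After 1 or 2 responses, the raw estimate and upper limit make low activity look better established than the design supports. These are plausible outcomes: at a true rate of 5% they have a combined probability of about 40%.

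**Working it through.** **Inputs.** Null 5%, target 20%, one-sided alpha 0.10, power 90%, n1 = 18, stop at 0 of 18, n2 = 14, N = 32 (Section 17.1); final cutoff at least 5 (Section 17.1, synopsis) or at least 4 (Section 5.2); 95% interval (Section 17.2), exact binomial (synopsis).

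**The plan's own figures.** The chance of stopping at 5% is 0.95^18 = 0.397, which agrees with the stated 40%. The chance of a positive trial is the sum over x1 ≥ 1 of Bin(x1; 18, p) × P(X2 ≥ c − x1; 14, p):

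| Cutoff c | Alpha at p = 5% | Power at p = 20% |
|---|---|---|
| At least 5 (17.1, synopsis) | 0.020 | 0.793 |
| At least 4 (5.2) | 0.072 | 0.901 |

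The stated 90% power is reproduced only with at least 4 of 32.

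**Bias of the raw rate.** The expected raw rate is [18p + 14p(1 − (1 − p)^18)]/32, so the bias is −(14/32) p (1 − p)^18.
- p = 5%: −0.4375 × 0.05 × 0.397 = −0.0087, about −0.9 point.
- p = 20%: −0.4375 × 0.20 × 0.0180 = −0.0016, about −0.16 point.

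**Unbiased estimate.** For x responses in 32, the UMVUE is Σ C(17, y−1) C(14, x−y) / Σ C(18, y) C(14, x−y), summed over the possible Stage 1 counts y ≥ 1.
- x = 1: 1/18 = 5.6%.
- x = 2: (14 + 17)/(252 + 153) = 31/405 = 7.7%.

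**Two-stage exact limits.** The lower 95% limit solves P(X1 ≥ 1 and X ≥ x) = 0.025. The upper limit solves 1 − P(X1 ≥ 1 and X ≥ x + 1) = 0.025. For x = 1 the upper-limit equation is (1 − p)^18 + 18p(1 − p)^31 = 0.025, which gives p = 19.4%. The ordinary equation, (1 − p)^32 + 32p(1 − p)^31 = 0.025, gives 16.2%.

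| Responses of 32 | Raw | UMVUE | Ordinary exact 95% | Two-stage exact 95% |
|---|---|---|---|---|
| 1 | 3.1% | 5.6% | 0.1–16.2% | 0.1–19.4% |
| 2 | 6.3% | 7.7% | 0.8–20.8% | 0.8–21.9% |
| 4 | 12.5% | 12.9% | 3.51–29.0% | 3.54–29.1% |
| 5 | 15.6% | 15.8% | 5.28–32.8% | 5.29–32.8% |

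**How likely the low counts are at p = 5%.** P(1 of 32) = 18 × 0.05 × 0.95^31 = 0.184. P(2 of 32) = 405 × 0.05² × 0.95^30 = 0.217. Together 0.40.

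**Coverage.** Summing the probabilities of all outcomes whose ordinary interval contains the true rate gives 96.2% to 98.8% at true rates of 5, 10, 15, 20 and 25%. On a fine grid the minimum is about 94.4%, near a true rate of 21%.

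**Where a positive result's 95% interval includes 5%.**

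| Result | Ordinary lower limit | Two-stage lower limit | Declared positive under |
|---|---|---|---|
| 5/32 | 5.28% | 5.29% | 17.1, 5.2 |
| 4/32 | 3.51% | 3.54% | 5.2 only |
| 5/33 | 5.11% | 5.12% | 17.1 count, 33 dosed |
| 5/34 | 4.95% | 4.97% | 17.1 count, 34 dosed |
| 5/35 | 4.81% | 4.83% | 17.1 count, 35 dosed |

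Rows above 32 take Stage 1 as 18 and the rest as Stage 2.

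**One-sided 90% lower bound.** Solving P(X1 ≥ 1 and X ≥ x) = 0.10 gives 3.6%, 5.6% and 7.8% at 3, 4 and 5 of 32. It first exceeds 5% at 4 of 32.

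**The case against.** The strongest reply is that the interval is descriptive. The trial is judged on a response count, no section uses the interval to decide, and the ordinary exact interval stays close to nominal coverage. At 4 and 5 of 32 the unbiased estimate differs from the raw rate by only 0.4 and 0.2 point. At 1 of 32 both upper limits lie below the 20% target, and at 2 of 32 both lie above it, so the adjustment changes neither reading against the target. Trials with 1 or 2 responses are negative under every stated cutoff. All of this stands and keeps the point small. It does not remove the shift of 2.4 points in the estimate and 3.2 points in the upper limit at 1 of 32, which is nearly free to correct.

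A reader might go further and infer that a trial declared positive will report an interval containing the 5% null, because a two-sided 95% interval is paired with a one-sided 10% test. The documents do not support that as a general claim. Under the cutoff in Section 17.1 and the synopsis, the smallest positive result is 5 of 32, and its exact interval excludes 5%. Overlap at 4 of 32 needs the conflicting cutoff in Section 5.2. Overlap at 5 of 34 or 35 needs a rule written for 32 evaluable patients to be applied to a larger dosed population. Ignoring the Stage 1 stop causes neither, since the two-stage 95% interval leaves both overlaps in place. A descriptive 95% interval beside a one-sided 0.10 count rule is not in itself an error.

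**Conclusion.** The point holds as a minor improvement to estimation and reporting. The planned summary ignores the Stage 1 stop. The consequence is a bias of about -0.9 point at a true rate of 5%, a visible understatement at 1 and 2 of 32, and a lowest coverage of about 94.4%; at the success boundary it is negligible. The trial's decision and error rates are unaffected. The figures assume stages of exactly 18 and 14, a stop only at 0 of 18, and the synopsis's exact binomial method where Section 17.2 is silent.

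Whether the interval can disagree with the decision is a separate question that depends on the unresolved cutoff and denominator. Those inconsistencies matter more than the estimator, because the at-least-5 rule has 79% power rather than 90%.

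**What to change.** 1. Reconcile the final cutoff across the synopsis, Section 5.2 and Section 17.1, and state whether the decision rule applies to 32 evaluable patients or to all dosed patients (up to 35).
2. In Section 17.2, report the UMVUE with a two-stage exact 95% interval computed from the actual stage sizes, and give the raw proportion alongside. Make the synopsis agree.
3. If the cutoff becomes at least 4 of 32, also report the two-stage one-sided 90% lower bound (3.6% at 3 of 32, 5.6% at 4 of 32), because the 95% interval at 4 of 32 (3.5% to 29.0%) includes the null.
4. If the cutoff stays at least 5 of 32, do not add that bound: it would exclude 5% at 4 of 32, a result declared negative.

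The estimation change costs a sentence or two in Section 17.2 and a few lines of code. The drawbacks are a less familiar estimator and slightly higher mean squared error at true rates of about 5% or less (0.00209 against 0.00191 at 5%, summing probability × (estimate − 0.05)² over all outcomes). It should be written in before the response data are analysed, so that the choice does not look driven by the result.
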